2.7 Analysis of the key secondary objective

There is no key secondary objective.

2.8 Analysis of secondary efficacy objective(s)

The analyses for objectives which are assessed up to a particular time (e.g. up to the patient's fifth birthday) will include data collected in both the Core and Extension studies. The secondary efficacy analysis will be based on Extension safety set.

No multiplicity adjustment will be used for the analysis of secondary variables.

2.8.1 Secondary endpoints

Continuous variables:

The following objectives will be assessed for the continuous variables below by using the same CMH test approach as the primary analysis with ROP zone at Core baseline as stratification factor.

- The comparison between ranibizumab 0.1 mg and laser with regard to the VA of the better- seeing eye at the patient's fifth birthday
- The comparison of ranibizumab 0.2 mg versus ranibizumab 0.1 mg with regard to the VA of the better-seeing eye at the patient's fifth birthday
- The three pairwise comparisons of treatment arms will be repeated with regard to the VA of the worse-seeing eye at the patient's fifth birthday

Again, one needs to be cautious interpreting the p-values when they show statistical significance and the point estimates indicate ranibizumab treatment is better than laser.

Recurrence of ROP is defined as ROP receiving any study intervention after the first study treatment of the Core study.

Binary variables:

- The absence of all ocular structural abnormalities (see below for the definitions) at or before the patient's 2 years' corrected age and fifth birthday.
- The absence of active ROP at 52 weeks post Core baseline

The CMH test with ROP Zone as assessed at the baseline of the Core study as stratification factor will be used for inference concerning binary secondary efficacy variables. Mantel-Haenszel odds ratios and their two-sided 95% confidence intervals will be presented. The rejection of the null hypothesis (equality of proportions) and the Mantel-Haenszel odds ratio being in favor of the hypothesized superior treatment should be interpreted with caution.

The absence of active ROP in both eyes is defined by the absence of all of the following features:

- Vessel dilatation of plus disease in at least 2 quadrants (some persisting tortuosity is allowed)

- Extra-retinal vessels extending from the retina into the vitreous and judged to be a sign of active ROP disease.

The absence is defined as the absence of both of the above individual components at a particular time point, e.g., at week 40.

The absence of all ocular structural abnormalities is defined by the absence of all of the following fundus features in both eyes at or before a particular time point, e.g., week 40 after the first study treatment in the Core study:

- Substantial temporal retinal vessel dragging causing abnormal structural features/
macular ectopia
- Retrolental membrane obscuring the view of the posterior pole
- Posterior retinal fold involving the macula
- Retinal detachment involving the macula

The absence is defined as the absence of the above individual components at all visits prior to and at a particular time point. Therefore, at least one presence of the above individual components at any visit prior to or at that time point is considered presence of ocular structural abnormalities. If at all visits up to that time point, the entry of at least one of the individual components is missing and none of the others indicates the presence of the disease feature, the subject will be considered as having missing record for this outcome.

The absence of each ocular structural abnormality considered individually in both eyes at or before a particular time point:

- Substantial temporal retinal vessel dragging causing abnormal structural features/
macular ectopia
- Retrolental membrane obscuring the view of the posterior pole
- Posterior retinal fold involving the macula
- Retinal detachment involving the macula
- Retinal detachment not involving the macula
- Pre-retinal fibrosis
- Optic disc pallor (from Visit 301/week 52 included onwards)
- Optic disc swelling (from Visit 301/week 52 included onwards)
- Pigmentary disturbance in the macula (from Visit 301/week 52 included onwards)
- Atrophic changes in the macula_(from Visit 301/week 52 included onwards)
- Low visual acuity testing:
Descriptive statistics will be provided for the best vision of the Low Visual Acuity Testing by treatment arm for subjects who have 0 or missing ETDRS letter scores at the 5th birthday visit by best/worst eye.

Other efficacy variables:

Descriptive statistics with 95% Clopper-Pearson exact confidence interval will be provided for these efficacy variables by treatment arm:

- The absence of all ocular structural abnormalities (see [Section 2.15](#) for the definitions) at or before 40 weeks post baseline visit in the Core study
- The recurrence of ROP up to 40 weeks post Core baseline
- The absence of active ROP at 40 weeks post Core baseline
- The absence of each ocular structural abnormality considered individually (see [Section 2.14](#) for the definitions) at or before the patient's 2 years' corrected age and at or before the patient's fifth birthday
- At the patient's 2 years' corrected age and fifth birthday
 - The refraction in each eye: Refractive error will be categorized into myopia (spherical equivalent of equal to or less than -0.25 dioptres) and high myopia (spherical equivalent of equal to or less than -5.00 dioptres). The percentage of patients with and without myopia, and with high myopia will be displayed.

If the entry of one of the above individual components is missing and the other indicates absence of the disease feature, the subject will be considered as having missing record for this outcome. Handling of missing values/censoring/discontinuations

No imputation of missing data will be used for the analysis of secondary variables unless specified in a scoring manual or similar.

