To evaluate the absence of ocular structural abnormalities at or before 40 weeks post baseline visit in the Core study, at the patient's 2 years' corrected age and fifth birthday	
Title: absence of all ocular structural abnormalities as listed in Section 2.8.1
 
Unit of measure: number and percentage of patients
 
Time frame: at or before V203 (Week 40) in the Core/ Extension study, at or before V302 (the patient's 2 years' corrected age), at or before V399 (the patient's fifth birthday)
 
Title: absence of each ocular structural abnormality as listed in Section 2.8.1 considered individually
 
Unit of measure: number and percentage of patients
 
Time frame: at or before week 40, at or before patient's 2 years' corrected age, at or before patient's fifth birthday

To evaluate the recurrence of ROP up to 40 weeks post baseline visit in the Core study	
Title: recurrence of ROP
 
Unit of measure: number and percentage of patients with recurrence of ROP
 
Description: Recurrence of ROP is defined as ROP receiving any intervention after the 1st study treatment in the Core study^d.
 
Time frame: up to 40 weeks postbaseline visit in the Core study

To assess the number of ranibizumab injections received in the treatment of patients with ROP up to and including 40 weeks post baseline visit in the Core study	
Title: number of ranibizumab injections
 
Unit of measure: number of ranibizumab injections
 
Description: as per title
 
Time frame: up to and including 40 weeks post baseline visit in the Core study

OBJECTIVE	Endpoint Title, Description and Reporting Time frame for analysis and Unit of measure
To evaluate the refraction in each eye at the patient's 2 years' corrected age and fifth birthday ^a	
Title: refraction in each eye Unit of measure: diopters Time frame: at patient's 2 years' corrected age, patient's fifth birthday

To evaluate the physical development at the patient's 2 years' corrected age and fifth birthday ^b	
Title: standing/sitting height, leg length, weight Unit of measure: centimeter, gram (as appropriate) leg length will be derived from standing/sitting height difference Time frame: at the patient's 2 years' corrected age, at the patient's fifth birthday
 
Title: head circumference Unit of measure: centimeter Time frame: at the patient's 2 years' corrected age

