To evaluate the health status at the patient's 2 years' corrected age and fifth birthday ^{b,c}	
Title: respiratory function^b Unit of measure: number and percentage of patients with oxygen supplementation; with presence of wheezing symptoms
 
Title: hearing function^c Unit of measure: number and percentage of patients with presence of hearing impairment
 
Title: duration of hospitalization after first hospital discharge home; weight at first hospital discharge home Unit of measure: days/months as appropriate; gram
 
Time frame: at the patient's 2 years' corrected age, at the patient's fifth birthday

OBJECTIVE	Endpoint Title, Description and Reporting Time frame for analysis and Unit of measure
	

- a - Variable corresponding to “ocular effects” in the plan for specific follow-up in the Pediatric Investigation Plan (EMA)
- b - Variable corresponding to “clinical outcomes” in the plan for specific follow-up in the Pediatric Investigation Plan (EMA)
- c - Variable corresponding to “neurodevelopmental outcomes” in the plan for specific follow-up in the Pediatric Investigation Plan (EMA)
- d - Supplementary laser treatments (as per CRFB002H2301 study protocol) are considered part of the complete laser treatment
- e - At the visit as close as possible to the patient’s fifth birthday

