2.1 Changes to the planned analyses in the protocol

The Extension study is conducted to fulfill regulatory requirements independent of whether the Core study succeeds on its primary objective or not. As such, Type I error and power control is not a feature of the Extension study design, and the results cannot be viewed within a valid inferential context. Thus, statistical significance cannot be inferred from any analyses based upon reaching specific significance thresholds. As a result, all hypotheses testing is not aimed to claim statistical significance or superiority of one treatment group against another, but needs to be interpreted with caution.

Patients may receive study treatment up to Week 40 only, while the study is purely observational beyond this time point. Therefore, results from the analysis of “recurrence of ROP up to 52 weeks post baseline visit in the Core study” (stated in protocol Section 9.5.1) would be identical to the results performed for “recurrence of ROP up to week 40 post baseline visit in the Core study”, since recurrence (defined as intervention, i.e. study treatment, received after baseline of the Core study”) remains unchanged and such analysis at week 52 is considered not meaningful.

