2.2.1 General definitions

Study treatment refers to study ranibizumab in both Core and Extension studies, and laser therapy in the Core study. (Please note that laser is a study treatment in the Core study but not a study treatment in the Extension study.) In this document, patient and subject are used interchangeably throughout the document.

A patient randomized to ranibizumab in the Core study can receive switch/rescue laser therapy in either eye; a patient randomized to laser therapy in the Core study can receive switch/rescue ranibizumab 0.2 mg in either eye. The change of treatment modality from laser to ranibizumab can occur at any time in the Core study and only in Epoch 1 of the Extension study, while the change of treatment modality from ranibizumab to laser can only occur in the Core study as only ranibizumab is available as study treatment in the Extension study. No further ranibizumab treatment can be administered to the eye after it has been switched to laser. The switch of study treatment occurs when the patient first receives a treatment modality other than the modality of the first study treatment in either eye, which can occur in the Core or Extension study period.

There are three treatment arms defined by the initial treatment received at baseline of the Core study:

- 0.2 mg Ranibizumab arm (same as Ranibizumab 0.2 mg arm)
- 0.1 mg Ranibizumab arm (same as Ranibizumab 0.1 mg arm)
- Laser treatment arm (same as Laser arm)

All results will be displayed by the initial treatment received at Core study baseline. If appropriate, within each of these three treatment arms, analyses may also be conducted separately for patients who received monotherapy or who switched treatment (by eye or by patient as applicable) during the Core study.

Two baselines are defined; Core baseline and Extension baseline. For statistical purposes, the last available non-missing values collected in study CRFB002H2301 or CRFB002H2301E1 prior to or on visit 201 will be considered to be the Extension baseline values. Core baseline will be used as baseline for both efficacy and safety analyses. The Extension baseline will be used for the demographic summary of the Extension study.

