2.5 Treatments (study treatment, rescue medication, concomitant therapies, compliance)

2.5.1 Study treatment / compliance

Exposure will be calculated for patients in the Extension safety set from Core baseline. Note that only study ranibizumab as collected in the Drug Administration Record (DAR) eCRF panel will be included. Treatments collected as a concomitant medication will not be included in the study medication analysis. Laser treatment is not a study treatment in the Extension study and therefore will not be collected in the DAR eCRF and will not be summarized here.

Exposure to ranibizumab is defined as the number of injections of ranibizumab received by worst/best eye (as defined in the Core study) and by patient.

The total number of ranibizumab injections will be summarized by worst/best eye and by patient by treatment arm. Summaries will be provided for the entire study period from Core baseline, and for Extension study period. (Note: summary will be summarized by initial treatment received at the baseline of the Core).

The duration of the observation period will be displayed for each treatment arm, and in the Extension study, and overall from Core study baseline.

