2.6 Analysis of the primary objective

2.6.1 Primary endpoint

The primary efficacy variable is the visual acuity (VA) in the better-seeing eye at the patient's fifth birthday as recorded by the investigator.

The primary efficacy analysis will be based on the Extension safety set.

Note that the ranibizumab 0.2 mg arm includes those patients that received ranibizumab 0.2 mg at baseline in the Core study. This includes patients that received laser treatment at a later date in either the Core or Extension study. Patients that permanently discontinue treatment with ranibizumab 0.2 mg are also included in primary efficacy analysis. However, patients for which the value of the primary variable is missing are excluded. A similar approach is taken for the ranibizumab 0.1 mg arm.

Similarly, the laser arm includes those patients that received laser at baseline in the Core study CRFB002H2301. This includes patients that received ranibizumab 0.2 mg treatment at a later date in either the Core or Extension study. Patients that permanently discontinue treatment with laser are also included in the primary efficacy analysis. However, patients for which the value of the primary variable is missing are excluded.

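### Recurrence of ROP is defined in two incompatible ways, and the reason for dropping its week-52 analysis holds only under the narrower definition

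*SAP*

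**What the plan says.** The SAP describes recurrence in three places.

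- **Section 1.2, Table 1-1:** "Recurrence of ROP is defined as ROP receiving any intervention after the 1st study treatment in the Core study". Footnote d is attached to this definition: "Supplementary laser treatments (as per CRFB002H2301 study protocol) are considered part of the complete laser treatment". The time frame is up to 40 weeks after Core baseline.
- **Section 2.8.1:** "Recurrence of ROP is defined as ROP receiving any study intervention after the first study treatment of the Core study". Footnote d is neither repeated nor cross-referenced.
- **Section 2.1:** "recurrence (defined as intervention, i.e. study treatment, received after baseline of the Core study". This gloss accompanies the decision to drop the week-52 recurrence analysis, which the SAP attributes to protocol Section 9.5.1. The reason given is: "Patients may receive study treatment up to Week 40 only, while the study is purely observational beyond this time point". From this the SAP concludes that the two time points would give the same result.

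Two further statements determine what these wordings mean in practice. Section 2.2.1 says that "laser is a study treatment in the Core study but not a study treatment in the Extension study", and Section 2.5.1 adds: "Laser treatment is not a study treatment in the Extension study and therefore will not be collected in the DAR eCRF". Section 2.6.1, describing the children who stay in the ranibizumab 0.2 mg arm for analysis, says: "This includes patients that received laser treatment at a later date in either the Core or Extension study". It takes a similar approach for the 0.1 mg arm.

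**The concern.** Whether the word *study* stands before *intervention* decides which children are counted. Extension laser is foreseen but is not study treatment, so the two definitions can classify the same child differently. The supplementary-laser exclusion is attached to only one of them.

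Recurrence is a listed secondary objective. It is reported by arm with exact 95% confidence intervals and appears in both interim analyses. The recurrence items in Section 2.15 point to no definition, so interim and final outputs could be programmed from different sections.

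The possible distortions differ by arm. Leaving out non-study interventions can understate recurrence, and counting supplementary laser can overstate it in the laser arm. The decision to drop the week-52 summary also rests on one of the two readings without saying so.

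**Working it through.** The SAP states no figure for this endpoint, so there is none to reproduce. The check applies each definition to every kind of later intervention that the SAP foresees.

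| Child's only intervention after first Core study treatment | Table 1-1 with footnote d | Section 2.8.1 as worded |
|---|---|---|
| Study ranibizumab re-treatment, or study switch treatment, in the Core study | counted | counted |
| Study ranibizumab in Epoch 1 of the Extension (re-treatment or switch from laser) | counted | counted |
| Supplementary laser in the Core study | not counted | counted if read literally, since laser is a Core study treatment |
| Laser or other non-study ROP therapy in the Extension, by week 40 | counted | not counted |
| The same therapy, first given in weeks 40 to 52 | counted, if the wording is applied at week 52 | never counted |

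**Which children move.** Only children with no other qualifying intervention change category; a child already re-treated or switched with study treatment counts under both rules. A ranibizumab-arm child given study laser in the Core study has already switched and counts either way. The supplementary-laser row can therefore reclassify children only in the laser arm.

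**Asymmetry under Section 2.8.1.** A laser-arm child who receives study ranibizumab in Epoch 1 is a recurrence. A ranibizumab-arm child whose only later intervention is laser in the Extension is not. A change of modality is counted in one direction and not in the other.

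**Week 52.** If only study treatment counts and none may be given after week 40, the cumulative count cannot change between weeks 40 and 52, and the reasoning in Section 2.1 is sound. If any intervention counts, an observational period does not rule out non-study therapy, and a first such therapy after week 40 would raise the week-52 count. The equality therefore follows only from the narrow rule.

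**Calendar windows, from Sections 1.1 and 2.1, assuming seamless roll-over at week 24:**

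- Part of the reporting window in which laser is non-study: 40 − 24 = 16 weeks; 16/40 = 40%.
- Period with no study treatment permitted before the dropped time point: 52 − 40 = 12 weeks.

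These are lengths of time, not effect sizes. The SAP gives no counts of non-study interventions or supplementary laser, so the number of children reclassified cannot be calculated.

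**The case against.** The best reply is that the SAP already shows which rule it means. Section 2.1 equates intervention with study treatment and Section 2.8.1, the analysis section, applies the same restriction. Table 1-1 could then be a summary cell that was not updated, and under the narrow rule the week-52 argument is correct. This is a fair guide to intent. It still leaves Table 1-1 contradicting the other two sections, and it does not remove the asymmetry between arms. Section 2.1 also counts from Core baseline rather than from after the first study treatment, so even the two narrow wordings do not match exactly.

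A second reply is that footnote d says what a complete laser treatment is. Supplementary laser would then belong to the first treatment and could not come after it, under either definition. That is a reasonable reading of the document as a whole. The conflict over supplementary laser arises only when Section 2.8.1 is read alone, so this is the weaker of the two divergences. A cross-reference would settle it.

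Third, Table 1-1 stops at week 40, so its wording reaches week 52 only if it is carried into the dropped protocol analysis. That limit stands, and the week-52 point is conditional on it.

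Finally, non-study therapies may be few, and concomitant medications and procedures are displayed elsewhere. That bears on size, which is unknown. It does not make the recurrence count unambiguous.

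**Conclusion.** The concern holds. Sections 1.2 and 2.8.1 give different counting rules for a reported secondary endpoint. They clearly diverge for non-study intervention in the Extension, and they diverge for supplementary Core laser if Section 2.8.1 is read without footnote d. The stated reason for dropping the week-52 summary is valid only under the narrow rule.

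Neither the size nor the net direction can be established from the SAP. The result rests on the SAP's own statements that laser is non-study in the Extension and may nevertheless be given there; how often is not stated. The protocol's definition was not available for this check.

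The consequence is limited. The endpoint is descriptive, no formal test depends on it, and active ROP at week 52 and structural outcomes are still analysed. It should be fixed because the same data could yield different recurrence proportions by arm depending on the section programmed.

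**What to change.** State one definition, consistent with the protocol, and use it in Sections 1.2, 2.1 and 2.8.1. Point the recurrence items in Section 2.15 to it.

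- **Preferred for reporting:** count any ROP intervention, study or non-study. Carry footnote d into Section 2.8.1. Derive the endpoint from the drug administration, concomitant medication and procedure records, and show recurrence treated with study intervention only as a breakdown. Then remove the equality argument from Section 2.1, and either reinstate the descriptive week-52 summary or justify dropping it on other grounds.
- **If the narrow rule is kept:** amend Table 1-1 and rename the endpoint so that the restriction is visible, for example recurrence treated with study intervention. State how supplementary laser is handled, and report non-study ROP interventions by arm beside it. The week-52 rationale can then stand.

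The cost is SAP wording and one derivation from records already collected. Reported recurrence counts may move in either direction.
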